Study Cigarettes. Using procedures similar to Strasser and colleagues commercially available Camel Crush cigarettes (R.J. Reynolds, Winston-Salem) will be used for both menthol and non-menthol smoking in Visit 2.⁶ We chose these because they contain a small, menthol-filled capsule that breaks open when squeezed and releases menthol into the cigarette. They are well suited to isolate menthol’s effects because there is no menthol flavor prior to squeezing, minimal menthol variation after crushing, and similar levels of nicotine, cotinine, and NNK, before and after crushing. They are also ideal because they are not popular among our typical participants (i.e., < 1 in 125 participants), based on analysis of PATH Wave 1 data, and have nicotine levels comparable to the very popular brands of Newport (0.8 mg) and Marlboro (0.8 mg). Thus, Camel Crush cigarettes will allow us to isolate menthol’s effects in the absence of cigarette loyalty or familiarity, and the other potential differences between cigarette types other than menthol level.

Study Procedures

Phase 1 Overview and Experimental Design

Phase 1 (Aim 1) will take place in the laboratory at Health Promotion Research Center (HPRC), in Oklahoma City, OK. A 2 (menthol preference: yes/no) X 2 (cigarette type: usual brand versus experimental cigarette) factorial design will be used with cigarette type as a within-subjects factor. After determining initial eligibility via telephone and/or online, \geq 12-hour abstinent smokers (CO-verified \leq 8 ppm) will attend each of 3 lab visits scheduled around the same time of day and separated by at least 48 hours (from start time

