Participants will be asked and reminded not to send PHI via email or any other unapproved system. Research data will only be collected and recorded via approved data collection systems (e.g. REDCap and mHealth Insight)

Laboratory Visit /Session 1: Baseline Assessment and Ad Libitum Smoking. Visit 1 (between-subjects) will measure absolute reinforcing value (ARV) of menthol vs non-menthol cigarettes via a 60-minute ad libitum smoking session of one's usual cigarette type (menthol or non-menthol). Subjective response (e.g., smoking satisfaction, craving reduction, psychological reward, sensory effects like throat hit), smoking exposure (CO boost), and behavior (topography: number of puffs, total time smoked) will be measured.

After completing the initial screening over the phone, participants will be informed of the study procedures and invited to the lab to complete the three laboratory visits (If in-person data collection is occurring and if they choose to come to the laboratory). During scheduling for Visit 1/Session 1, they will be reminded to bring at least two of their cigarettes to the first study visit and will be asked to abstain from nicotine and tobacco products, and any other combustible product (e.g., cannabis) for at least 12 hours prior to each study visit. If they are going to attend an in-person session, they will be reminded to wear a mask and that they will be asked about any changes in the COVID-19 screener since they were first asked. If an individual selects virtual study sessions, they will be asked to complete the visit 1 procedures remotely using a remote topography device and iCO carbon monoxide reader to confirm smoking recency. In-person participants will provide a breath sample to measure carbon monoxide levels and asked when the last time they smoked a cigarette was. We will use password protected video conferencing to allow study staff to assist participants and complete this and the below procedures.

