After completing questionnaires, ARV will be measured by having participants smoke their usual brand of cigarette (*ad libitum*), which they will be instructed to bring with them to the first study visit. They will smoke through a mouthpiece of the Cress Smoking Topography Device, during a 60-minute smoking Visit or the SODIM Smoking Puff Analyzer Mobile SPA-M The CReSS or SODIM instrument will record puff volume, duration and velocity and inter-puff interval for each puff and their aggregate averages.⁷⁻¹⁰ Puff topography measures will be used to examine whether increased puff volume, duration, and lower inter-puff interval differ across menthol and non-menthol cigarettes. Before and after smoking, heart rate and blood pressure will be collected (if session is taken in person); exhaled carbon monoxide (CO boost), and subjective response to smoking (craving reduction, psychological reward, satisfaction, sensory effects) using the Cigarette Evaluation Questionnaire (CEQ). Exhaled carbon monoxide will be collected and measured in ppm immediately before and after smoking. At the completion of Visit 1, participants will be paid for the visit, and scheduled for study visits (V2 and V3).

Laboratory Visit or Session 2: Sampling Experimental Cigarettes and Cross-Price Elasticity Task. Participants will confirm abstinence by being asked the last time they smoked a cigarette in addition to providing a carbon monoxide measurement (CO \leq 8 ppm). Visit/Session 2 (within-subjects) will familiarize participants with the experimental cigarette (Camel Crush) by having them take a minimum of 3 and up to 5 puffs each of a menthol and non-menthol version (counterbalanced) and complete subjective ratings,

smoking exposure (CO boost), and behavior (topography: total time smoked). There will be a 20 minute washout period between each cigarette smoked, per our consultant's ([name]) paradigm protocol¹¹⁻¹⁴. Before and after smoking heart rate and blood pressure will be recorded (if session is taken in person), approximately 5 minutes after smoking subjective response, and CO boost will be recorded. After another 20 minute wait period from the last cigarette puff.

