Using a concurrent schedule, participants will be able to switch from working on one screen to the other as often as they desire. Consistent with relative reinforcement paradigms, the reinforcement schedule in the non-menthol earning screen will remain constant at a fixed ratio FR-25 (25 targets achieved to earn a point) while the reinforcement schedule for the menthol cigarette will increase (require more effort) with a progressive ratio schedule of PR-25 x over 10 trials, such that 25, 50, 75, 100, 125, 150, 175, 200, 225, and 250 targets have to be "hit" to earn a point.

The choice task determines how reinforcing menthol cigarettes are relative to non-menthol cigarettes (of the same brand) by the participant's willingness to work increasingly harder for puffs of a menthol cigarette vs nonmenthol cigarette. Reinforcement will be defined by the breakpoint, or the highest trial (out of 10 trials) that will be completed for menthol cigarette puffs.

The computer task will be performed until 10 trials are completed and a total of 10 points (or puffs) are accumulated. Per paradigm protocol, cigarette puffs earned are taken at the end of the procedure.²¹ Following the choice task, participants will be able to smoke the cigarette puffs they earned (up to 10 puffs). As in Visits 1 and 2, subjective response (e.g., smoking satisfaction, craving reduction, psychological reward, sensory effects like throat hit), smoking exposure (CO boost), and behavior (topography: number of puffs, total time smoked) will be measured.

To ensure that choice task responses are based on reinforcer preference rather than departure from the laboratory, the choice task will be followed by a 30-minute wait in the laboratory (if the session is taken in person). If the session is taken remotely, there may not be a 30-minute wait period. During this 30-minute wait period, participants will be queried about potential reactivity (i.e., behavior change or increased awareness of behavior and attitudes) to the laboratory visits with a brief survey. They will then be given instructions for the EMA phase of the study (Phase 2). During this training, participants will complete a practice survey from their phone. They will be given a wallet sized reference card containing the date range of the monitoring period, the lab study phone number, and a paper copy of the EMA questions and response options.

Table 2. Phase 1 Measures and Schedule of Events Under Normal Operating Procedures

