A 2 (menthol preference) X 2 cigarette type (usual brand versus experimental brand) mixed ANOVA will be conducted to examine main effects and interactions on the outcomes of interest. Models will examine cigarettes per day (CPD), nicotine dependence, race/ethnicity, gender, and age of smoking onset as potential covariates. Factors related to Phase 1 drop-out will be examined as potential covariates. If nicotine and CPD are collinear, the most significant predictor of the outcome will be retained in the model. Significant interactions will be followed up with individual contrasts of cell means using Fisher’s Least Significant Difference tests. In exploratory analyses, a 2 (menthol preference) X 4 (race/ethnicity: White, Black, Other, Hispanic) between-subjects ANOVA and a 2 (menthol preference) x 2 (gender) between subject ANOVA will be conducted separately for the BL Visit to evaluate differential reactions to own brand cigarette smoking by race/ethnicity and by gender. Comparison of own brand/usual brand and experimental cigarette ratings will also be made to determine the perceived similarity of the experimental cigarette to one’s own brand and as a function of gender and race/ethnicity. NOTE: We expect that ratings of appeal/reinforcement for the experimental cigarettes will be lower than ratings of appeal for usual brand. Ratings of experimental cigarettes will be examined as a potential covariate in Aim 3 models. Age of smoking initiation will also be examined as a potential covariate. Covariates with $p < .05$ will be retained in final models.

Phase 2/Aim 2 Analyses

Primary Outcomes: (a) within-day subjective response (craving reduction, satisfaction, psychological reward, physical sensations like throat grab) to the most recent cigarette smoked (menthol vs non-menthol); (b) betweenday subjective response.

Secondary Outcomes: (a) Aggregate ratings of subjective response (over the course of 14 days) by baseline menthol brand preference (at the person-level, rather than by day); (b) changes over the course of days (creating an average change score for each person); (c) within-person variability by calculating the standard deviation of daily cigarette reward, satisfaction, craving reduction, and throat hit ratings for each person; (d) cigarettes per day (within-day, over days); and (e) craving intensity (within-day, over days).

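### In the Aim 1 usual-versus-experimental comparison, the cigarette is confounded with the amount smoked

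*Combined protocol and SAP*

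**What the plan says.** The Phase 1/Aim 1 Analyses section of the Data Analysis Plan states: "A 2 (menthol preference) X 2 cigarette type (usual brand versus experimental brand) mixed ANOVA will be conducted to examine main effects and interactions". The Phase 1 Overview says that a 2 × 2 "factorial design will be used with cigarette type as a within-subjects factor", so each participant supplies both levels. The analysis section also compares the two sets of ratings to see how alike the cigarettes seem, and says in advance that the experimental cigarette is expected to rate lower.

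The amount smoked is set differently at each visit:

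- **Visit 1, usual brand.** This visit "will measure absolute reinforcing value (ARV) of menthol vs non-menthol cigarettes via a 60-minute ad libitum smoking session". No puff limit is stated. When participants are scheduled, "they will be reminded to bring at least two of their cigarettes to the first study visit".
- **Visit 2, Camel Crush.** Participants "take a minimum of 3 and up to 5 puffs each of a menthol and non-menthol version (counterbalanced". "There will be a 20 minute washout period between each cigarette smoked".
- **Visit 3, usual brand again.** After the choice task, "participants will be able to smoke the cigarette puffs they earned (up to 10 puffs".

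The Phase 1 schedule (Table 2) lists exhaled CO, the rating questionnaires and puff topography at all three visits. The candidate covariates are cigarettes per day, dependence, race/ethnicity, gender, age of onset and factors related to drop-out. The named ones all describe the person; none describes how much was smoked in the session.

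**The concern.** Total puffs, time smoked and CO boost depend directly on how much is smoked, and ratings of satisfaction, reward and craving reduction may do so too. The protocol itself treats recent smoking as influential. It requires 12 hours of abstinence to control for it, and it adds a wait before the Visit 2 purchase task to limit satiation. Smoking before each session is therefore controlled, but the amount smoked within it is not.

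If the predicted lower rating for Camel Crush appears, the analysis cannot say whether participants liked the cigarette less or simply had less of it. The similarity comparison has the same problem: two identical cigarettes could come out as dissimilar. The interaction is exposed as well, because the Visit 1 amount is self-chosen and could differ by menthol preference, while the Visit 2 amount is nearly fixed. What is at stake is a feature of the protocol being reported as a brand effect.

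**Working it through.** **Is there a figure to reproduce?** No. The documents give 125 per group but no alpha, power, effect size or SD, and no ad libitum puff count. The check is therefore a comparison of the sessions, followed by two illustrations on stated assumptions.

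**Step 1: exposure at each level of the factor.**

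| Level | Visit | Amount smoked |
|---|---|---|
| Usual brand | 1 | 60 minutes, self-chosen, no cap stated |
| Experimental, each version | 2 | 3-5 puffs; the second version 20 minutes after the first |
| Usual brand, alternative source | 3 | up to 10 earned puffs, menthol and/or non-menthol |

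The analysis section does not name the visit that supplies the usual-brand level. Visit 1 is the natural reading. Visit 3 would not be matched either: at its maximum it allows 10/5 = 2 to 10/3 = 3.3 times the puffs of one Camel Crush version.

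**Step 2: possible size of the puff gap.** Assume 10-15 puffs per cigarette (not in the documents).

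- One usual-brand cigarette against one Camel Crush version: 10/5 = 2 to 15/3 = 5 times.
- Two usual-brand cigarettes: 20/5 = 4 to 30/3 = 10 times. Bringing two cigarettes does not mean smoking two, so this is an upper scenario.
- One usual-brand cigarette against the whole of Visit 2 (6-10 puffs): 10/10 = 1.0 to 15/6 = 2.5 times.

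These ratios apply to puff count only.

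**Step 3: what an exposure-only shift would do to the tests.** Suppose the cigarettes are equally liked and the amount smoked alone moves the rating by d SD. Assume 250 completers, two-sided alpha 0.05, a normal approximation and within-person correlation ρ.

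- Main effect: SE = √(2(1−ρ)/250).
- Interaction, with the shift in one preference group only: SE = √(2(1−ρ) × 2/125).
- Chance of significance: Φ(d/SE − 1.96) + Φ(−d/SE − 1.96).

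Worked case, ρ = 0.5 and d = 0.2. For the main effect, SE = √(1/250) = 0.0632 and d/SE = 3.16, giving 88.5%. For the interaction, SE = √(2/125) = 0.1265 and d/SE = 1.58, giving 35.3%.

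| d (SD) | Main effect, ρ = 0.3 / 0.5 / 0.7 | Interaction, ρ = 0.3 / 0.5 / 0.7 |
|---|---|---|
| 0 | 5% / 5% / 5% | 5% / 5% / 5% |
| 0.1 | 27% / 35% / 53% | 10% / 12% / 18% |
| 0.2 | 76% / 89% / 98% | 27% / 35% / 53% |
| 0.3 | 98% / 99.7% / 100% | 52% / 66% / 87% |

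If the shift is the same in both groups it cancels from the interaction, which stays at 5%.

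**Step 4: which comparisons do not cross the mismatch.**

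- The absolute reinforcing value contrast is between groups at Visit 1, where everyone smokes the usual brand ad libitum.
- The menthol breakpoint comes from responding in the Visit 3 choice task, before the earned puffs are smoked.
- The cross-price elasticity comes from a hypothetical purchase questionnaire.
- Menthol and non-menthol Camel Crush share one puff limit in counterbalanced order.

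**The case against.** The strongest reply is that little rests on this contrast. The three Aim 1 primary outcomes, as defined, do not cross the mismatch, and both preference groups follow the same protocol. The plan already expects Camel Crush to rate lower, and nothing depends on showing similarity. The amount smoked at Visit 1 is also partly a response to the cigarette, not pure nuisance. Even the direction of any rating bias is open, since an hour of free smoking may satiate. All of this stands. It limits the reach of the point but does not remove it: the plan still tests the factor and interprets the difference as resemblance between cigarettes. A bias in the opposite direction could hide a real difference.

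A reader might infer more than the documents support:

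- *That Camel Crush no longer isolates menthol.* The Study Products section rests that claim on other grounds: no menthol flavor before the capsule is crushed, similar nicotine, cotinine and NNK before and after, and low familiarity. The comparison between the two versions is matched on puff limit.
- *That CO boost and time smoked differ by the puff ratio.* Nothing in the documents supports proportionality, and time smoked also includes the gaps between puffs.
- *That a usual-versus-experimental test of puff count is explicitly planned.* The outcome list words puff count as menthol against non-menthol, and the Visit 2 text names only total time smoked. The ANOVA sentence leaves its outcomes open, so the plan should exclude this test rather than be charged with specifying it.

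**Conclusion.** The point holds for the cigarette-type main effect and for the similarity comparison: both combine the cigarette with the amount smoked and cannot be read as a brand difference. The interaction is valid only if the usual-minus-experimental exposure gap is the same in both preference groups, which the design does not ensure.

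The mismatch itself is certain from the text; the size of the bias is not known. The illustration shows that small shifts would be enough, but it rests on assumed completers, correlation and shift, and the documents give no relation between puffs and ratings. The point should be corrected before analysis. It does not call the primary Aim 1 outcomes into question.

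**What to change.** Change the analysis plan only. State which visit supplies the usual-brand level, and for every usual-versus-experimental comparison:

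1. Limit topography to the same number of initial recorded puffs at each visit (the first 3-5, matched to the number taken of the Camel Crush version), with the order of that version in the model. The Visit 1 text says the devices record each puff. Confirm that puff-level records also exist for Visit 2, where Table 2 lists topography.
2. Do not test CO boost, total puff count or total time smoked on this factor. Keep them for between-group comparisons within a visit.
3. Report the rating difference and the similarity comparison as a session difference (cigarette plus amount smoked), not as evidence for or against brand similarity. Add a sensitivity analysis of the interaction using recorded Visit 1 puff number or volume. Say that this cannot fully separate the two, because puff ranges may barely overlap and puffing is itself a response to the cigarette.

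The cost is plan wording and modest programming, fewer outcomes on this contrast and a narrower conclusion from it. Pausing Visit 1 after a few puffs for a matched reading is not recommended: it would interrupt the ad libitum session that supplies the first primary outcome and would make earlier and later Visit 1 data non-equivalent.

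### In the Phase 1 mixed ANOVA, the usual-versus-experimental main effect cannot be separated from visit or procedure, so it should be reported descriptively

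*Combined protocol and SAP*

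**What the plan says.** All references are to the combined protocol and SAP. Under Phase 1 Overview and Experimental Design, a 2 x 2 "factorial design will be used with cigarette type as a within-subjects factor". The Visit 1 section says "ARV will be measured by having participants smoke their usual brand of cigarette", in a 60-minute ad libitum session. Study Products says that Camel Crush "will be used for both menthol and non-menthol smoking in Visit 2", and no other visit uses it. At Visit 2 participants "take a minimum of 3 and up to 5 puffs each of a menthol and non-menthol version (counterbalanced"). That is the only counterbalancing in Phase 1, and it concerns the two Camel Crush versions, not usual against experimental.

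Phase 1/Aim 1 Analyses then specifies: "A 2 (menthol preference) X 2 cigarette type (usual brand versus experimental brand) mixed ANOVA will be conducted to examine main effects and interactions". The candidate covariates are person-level characteristics, factors related to Phase 1 drop-out and age of smoking initiation. No visit or session term is listed. The same section will compare own-brand with experimental ratings to judge how alike the cigarettes seem, and adds: "We expect that ratings of appeal/reinforcement for the experimental cigarettes will be lower than ratings of appeal for usual brand".

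The only order adjustment is under Phase 2/Aim 2 Analyses. It concerns which phase came first, not the order of visits within Phase 1.

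**The concern.** The two levels of the within-person factor are observed at different visits, in one fixed order. Anything that moves everyone's ratings between the first and second sessions is therefore counted as cigarette type. Possible causes are growing used to the mouthpiece and rating forms, or a second 12-hour abstinence. The procedure also changes between the visits, from an hour of free smoking to a few puffs of each version, and this is aliased in the same way.

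At stake is what can be said about the experimental cigarette against the usual brand. The plan predicts lower ratings for the experimental cigarette. A shared decline would produce that result with no difference between the cigarettes, and a shared rise would hide a real one. Readers may also lean on the similarity comparison when interpreting the Visit 2 data.

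**Working it through.** The text supplied gives no power, effect size or SD, so there is no planned figure to reproduce. The plan also does not say outright which visit supplies the usual-brand ratings. Visit 1 is the natural reading, because absolute reinforcing value is defined there and the exploratory own-brand ANOVAs are tied to the baseline visit.

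**1. Aliasing.** The model is rating = mean + preference + type + preference x type + person + error. With usual brand at Visit 1 and experimental at Visit 2 for all, the type column equals the visit column. For 250 people, the design matrix with person effects, type and type x preference has 252 columns and rank 252. Adding visit gives 253 columns, and the rank stays 252. For comparison, alternating the session order within each preference group gives rank 253 of 253.

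**2. Main effect under a shared shift.** Let s be the shift in rating SDs, rho the within-person correlation and N the number completing both visits.

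- SD of the within-person difference = sqrt(2(1 - rho)), which is 1 rating SD at rho = 0.5.
- Noncentrality = s x sqrt(N) / sqrt(2(1 - rho)), with N - 2 degrees of freedom and two-sided alpha 0.05.
- Example: s = 0.1, N = 250, rho = 0.5 gives 0.1 x 15.81 = 1.58, a rejection rate of 35%.

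The values of s, rho and alpha are assumptions. N = 250 is the planned 125 + 125. Rejection rates with no true cigarette difference, at rho = 0.5:

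| Shared shift | N = 250 | N = 200 | N = 150 |
|---|---|---|---|
| 0 | 5% | 5% | 5% |
| 0.1 SD | 35% | 29% | 23% |
| 0.2 SD | 88% | 80% | 68% |

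At 0.1 SD and N = 250, a normal approximation gives 27% for rho = 0.3 and 53% for rho = 0.7. N = 250 is a ceiling. Under Potential Risks, participants under 21 receive only session 1 of the laboratory visits until approval is obtained. Under Study Design, those enrolled during COVID-19 restrictions return for Phase 1 only if still interested and eligible.

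**3. Interaction.** It is the difference between the groups' mean within-person changes. A shift common to both groups cancels: in 20,000 simulated trials, rejection was 4.9%, 5.0% and 4.6% at shifts of 0, 0.2 and 0.3 SD, with a mean estimate near zero. The between-group preference effect is free of a common shift for the same reason.

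A shift that differs by group does not cancel. At rho = 0.5 the interaction's standard error is sqrt(1/125 + 1/125) = 0.126. A differential shift of 0.2 SD then has noncentrality 0.2/0.126 = 1.58, again about 35% rejection.

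**The case against.** The strongest reply is that little depends on this contrast. The primary outcomes in Phase 1/Aim 1 Analyses are the between-group comparison at Visit 1, the choice-task breakpoint at Visit 3 and cross-price elasticity from a purchase task. The hypotheses compare menthol with non-menthol smokers. No decision rule is attached to the brand main effect, and Aim 3 takes the experimental ratings, not this contrast, as a possible covariate. All of that stands, and it limits the point's importance. A reader might infer that the Aim 1 primary results are compromised; the documents do not support that.

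It is also fair that visits are standardised on abstinence, time of day and spacing, and that the size and direction of any shift are unknown. Familiarity could raise ratings and work against the predicted result. The rates above show sensitivity to a shift; they do not show that one exists.

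Two remedies are tempting. One is to add a visit term, which step 1 shows cannot be estimated. The other is to bring in Visit 3, where usual-brand puffs are rated again ("As in Visits 1 and 2, subjective response" is measured there). Those puffs, at most 10, are earned in a work task and may mix flavors, so a Visit 3 minus Visit 1 slope carries its own procedure change. Keeping only people whose earned puffs were all of their preferred flavor selects on choice-task behavior, and unevenly. Ten menthol points cost 25 + 50 + ... + 250 = 1,375 targets, against 10 x 25 = 250 for non-menthol. Visit 3 does not repair the contrast.

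**Conclusion.** The point holds with a limited scope. Taking usual-brand ratings from Visit 1, the cigarette-type main effect and the similarity comparison estimate cigarette type plus visit plus procedure, and no analysis of those two visits can divide them. This follows from the design and needs no assumption about size.

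The size does rest on assumptions. With no true cigarette difference, correlation 0.5 and two-sided alpha 0.05, a shared shift of 0.1 SD gives a significant main effect in about 23% to 35% of trials, and 0.2 SD in about 68% to 88%, for 150 to 250 completers. The preference effect and the preference x cigarette type interaction are unbiased by a common shift. The interaction is protected only if visit and procedure effects are equal in the two groups.

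**What to change.** In Phase 1/Aim 1 Analyses:

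1. State that the usual-brand ratings in the 2 x 2 model come from Visit 1.
2. State that the cigarette-type main effect and the similarity comparison reflect cigarette type, visit and procedure together. Report them descriptively, as an estimate with an interval and no claim of a cigarette effect.
3. Base Aim 1 inference from this model on the preference and preference x cigarette type terms. State that the interaction assumes equal visit and procedure effects in the two preference groups.

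This costs a few sentences and no new data. The downside is that the main effect no longer supports an inferential claim, including a formal test of the expectation that the experimental cigarette rates lower. Counterbalancing the session order would make visit estimable, but it would be a design change and would leave the difference in procedure in place.
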